## PDQ-39 Summary Index and Score by Domain

Visit	Scheduled Study Time	Visit Windows	
		Number of days after administration	Number of days after the end of administration
Baseline (prior to TVP-1012 administration)	Number of days after administration: -1	-22 ~ -1	
Week 14	Number of days after administration: 98	1 ~ 139	< 8
Week 26	Number of days after administration: 182	140 ~ 230	< 8
Week 40	Number of days after administration: 280	231 ~ 321	< 8
Week 52	Number of days after administration: 364	322 ~ 385	< 8
At end of administration		1 ~ 385	< 8

## Clinical Laboratory Tests

Visit	Scheduled Study Time	Visit Windows	
		Number of days after administration	Number of days after the end of administration
Baseline (prior to TVP-1012 administration)	Number of days after administration: -1	-22 ~ -1	
Week 3	Number of days after administration: 21	1 ~ 31	< 8
Week 6	Number of days after administration: 42	32 ~ 69	< 8
Week 14	Number of days after administration: 98	70 ~ 118	< 8
Week 20	Number of days after administration: 140	119 ~ 160	< 8
Week 26	Number of days after administration: 182	161 ~ 192	< 8
Week 29	Number of days after administration: 203	193 ~ 213	< 8
Week 32	Number of days after administration: 224	214 ~ 251	< 8
Week 40	Number of days after administration: 280	252 ~ 300	< 8
Week 46	Number of days after administration: 322	301 ~ 342	< 8
Week 52	Number of days after administration: 364	343 ~ 385	< 8

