8.1.3 Dose and Regimen

The administration of the study medication will start on the day after VISIT 8 and the subjects will be orally administered 1 tablet of TVP-1012 1.0 mg once daily before or after breakfast (at the same timing with the preceding study).

The investigator or its designee will supply sufficient amount of the study medication required during the period between study visits. Subjects will be instructed to take study medication in the morning of study visits* and to bring unused study medications and blister sheets to the site at each study visit. Also, compliance of the study medication from the last study visit will be checked by the investigator or sub-investigator (see Section 9.2).

* For the day the serum chemistry is scheduled, the study medication must be taken without having breakfast. In this case, deviation from the timing of dose (not before or after breakfast) will be permitted.

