Appendix A Schedule of Study Procedures

Study Week ^(a)	Treatment period						W52/ Early Termination ^(b)
	W26	W29	W32	W36	W40	W46	
VISIT Number ^(c)	8	9	10	11	12	13	14
Study Day ^(d) (Day)	182	203	224	252	280	322	364
Visit Windows ^(d) (Days)	175 to 189	196 to 210	217 to 231	245 to 259	273 to 287	315 to 329	357 to 371
Informed consent	X ^(e)						
Inclusion/exclusion criteria	X						
Physical examination	X ^(f)	X	X	X	X	X	X
Skin examination	X ^(f)						X
Weight	X ^(f)				X		X
Vital signs	X ^(f)	X	X	X	X	X	X
Concomitant medications	X ^(f)	X	X	X	X	X	X
Clinical laboratory tests ^(g)	X ^(f)	X	X		X	X	X
ECG	X ^(f)				X		X
MDS-UPDRS	X ^(f)		X	X	X	X	X
QOL assessment	X ^(f)				X		X
Drug compliance	X ^(f)	X	X	X	X	X	X
Dispense investigational drug	X	X	X	X	X	X	
AE assessment ^(h)	X ^(f)	X	X	X	X	X	X

(a) The study visit weeks in this study will be counted from the start of the treatment period in the preceding study.

(b) For subjects withdrawn from the study after the initiation of the investigational drug in this study and before Week 52 of the treatment period, the tests, observations, and assessments scheduled for Week 52 of the treatment period should be performed within 7 days following discontinuation of treatment, whenever possible (the day of the last dose regarded as 0 day).

(c) Visit numbers in this study will be continued from the preceding study.

(d) Day 1 is defined as the day of first study medication administration for the treatment period in the preceding study.

(e) Informed consent for this study must be obtained prior to tests, observations, and assessments at Week 26 of the treatment period in the preceding study.

(f) Results of the tests, observations, and assessments at Week 26 of the treatment period in the preceding study will be used also for this study.

(g) To be measured after fasting for at least 8 hours whenever possible. Women of childbearing potential will undergo pregnancy test as well.

(h) AE collection in this study will begin at the initiation of the investigational drug in this study, and continued until Week 52 of the treatment period or early termination. AEs occurring between the final assessment in the preceding study and the initiation of the investigational drug in this study will be captured by the preceding study. AEs that occurred during the preceding study and persisted into this study will be followed up in this study as well.

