## Glossary

- Descriptive statistics:

Number of subjects, mean, standard deviation, maximum, minimum, and quartiles

- MAV:

Markedly Abnormal Value

- Treatment groups in the preceding study:

TVP-1012 1 mg and placebo groups in the preceding study. However, they are shown as “1 mg ->1 mg group” and “P ->1 mg group” respectively in this statistical analysis plan.

- Study drugs for treatment period in both studies:

Study drug for treatment period in the previous study and study drug in this study

- Number of days after administration (days):

- A) For the analyses based on the data after administration of TVP-1012

The day before the day of first TVP-1012 administration is shown as Day -1 and the day of first TVP-1012 administration as Day 1. That is, shown as follows:

[If the treatment group in the preceding study is 1 mg ->1 mg group]

Day before the day of first study drug administration for the treatment period in the preceding study:	Day -1
Day of first study drug administration for the treatment period in the preceding study:	Day 1

[If the treatment group in the preceding study is P ->1 mg group]

Day before the day of first study drug administration in this study:	Day -1
Day of first study drug administration in this study:	Day 1

- B) For the analyses based on the data after study drug administration for the treatment period in the preceding study

The day before the day of the first study drug administration for the treatment period in the preceding study is shown as Day -1 and the day of the first study drug administration for the treatment period in the preceding study as Day 1.

- Number of days after the end of administration (days):

Day 1 is defined as the day following the later of “day of the last study drug administration for the treatment period in the preceding study” or the “day of the last study drug administration in this study.”

- Protocol Deviations:

Protocol deviations in this study, unless otherwise specified.

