### Definition of Visit Window

#### A) For the analyses based on the data after administration of TVP-1012

For each test, observation, and evaluation items, evaluable data (i.e., non-missing and acceptable according to the Handling Rules for Analysis Data) will be handled according to the following rules. However, the number of days after administration and number of days after the end of administration will be the contents of “For the analyses based on the data after administration of TVP-1012” in the Glossary.

Among the evaluation points, at points other than at the end of administration, evaluable data within the visit window will be used. If more than one evaluable data lies within the same visit window, the examinations, observation, and assessments with the Study Time closest to the scheduled Study Time will be used. If there are two observations equidistant to the scheduled Study Time, the later observation will be used. The size of difference from the Study Time will be determined based on the number of days after administration.

Among the evaluation points, at the end of administration, the data with the largest number of days after administration will be used among the evaluable data within the visit window.

MDS-UPDRS Part I, II, III, and IV Total Scores, MDS-UPDRS Part II + Part III Total Score, MDS-UPDRS Tremor, Muscle Rigidity, and Akinesia/Bradykinesia Scores, and MDS-UPDRS Individual Scores

Visit	Scheduled Study Time	Visit Windows	
		Number of days after administration	Number of days after the end of administration
Baseline (prior to TVP-1012 administration)	Number of days after administration: -1	-22 ~ -1	
Week 6	Number of days after administration: 42	1 ~ 55	< 8
Week 10	Number of days after administration: 70	56 ~ 83	< 8
Week 14	Number of days after administration: 98	84 ~ 118	< 8
Week 20	Number of days after administration: 140	119 ~ 160	< 8
Week 26	Number of days after administration: 182	161 ~ 202	< 8
Week 32	Number of days after administration: 224	203 ~ 237	< 8
Week 36	Number of days after administration: 252	238 ~ 265	< 8
Week 40	Number of days after administration: 280	266 ~ 300	< 8
Week 46	Number of days after administration: 322	301 ~ 342	< 8
Week 52	Number of days after administration: 364	343 ~ 385	< 8
At end of administration		1 ~ 385	< 8

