## Vital Signs

Visit	Scheduled Study Time	Visit Windows	
		Number of days after administration	Number of days after the end of administration
Baseline (prior to TVP-1012 administration)	Number of days after administration: -1	-22 ~ -1	
Week 3	Number of days after administration: 21	1 ~ 31	< 8
Week 6	Number of days after administration: 42	32 ~ 55	< 8
Week 10	Number of days after administration: 70	56 ~ 83	< 8
Week 14	Number of days after administration: 98	84 ~ 118	< 8
Week 20	Number of days after administration: 140	119 ~ 160	< 8
Week 26	Number of days after administration: 182	161 ~ 192	< 8
Week 29	Number of days after administration: 203	193 ~ 213	< 8
Week 32	Number of days after administration: 224	214 ~ 237	< 8
Week 36	Number of days after administration: 252	238 ~ 265	< 8
Week 40	Number of days after administration: 280	266 ~ 300	< 8
Week 46	Number of days after administration: 322	301 ~ 342	< 8
Week 52	Number of days after administration: 364	343 ~ 385	< 8

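### In the P->1 mg group, an on-schedule VISIT 14 laboratory or vital-sign value can be filed as Week 29, leaving that subject's Week 26 value empty

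*SAP*

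**What the plan says.** Two clocks are in use.

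- **Protocol clock.** Appendix A of the protocol counts study days from the preceding study: "Day 1 is defined as the day of first study medication administration for the treatment period in the preceding study". Its windows for VISITs 8 to 14 are "175 to 189 196 to 210 217 to 231 245 to 259 273 to 287 315 to 329 357 to 371", which is the nominal day plus or minus 7 at each visit.
- **TVP-1012 clock.** For P->1 mg, the SAP Glossary restarts the count at the first extension dose, labelling the day before the "day of first study drug administration in this study: Day -1", with the dosing day as Day 1. Protocol 8.1.3 fixes when that is: "The administration of the study medication will start on the day after VISIT 8".

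In SAP Definition of Visit Window A), one set of windows serves both groups. The laboratory table has "Week 3 Number of days after administration: 21 1 ~ 31" at the start and "Week 29 Number of days after administration: 203 193 ~ 213" after Week 26. The vital-sign table has "Week 26 Number of days after administration: 182 161 ~ 192". The MDS-UPDRS table, which has no Week 29 visit, has "Week 26 Number of days after administration: 182 161 ~ 202".

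The MDS-UPDRS and PDQ-39 tables end with an at-end-of-administration row. The laboratory and vital-sign tables do not. SAP 3.2.1.1, 3.2.1.2 and 3.2.2.1 list visits to Week 52 by preceding-study group, with no cap at Week 26 for P->1 mg. Protocol 6.2.3 plans 26 weeks of TVP-1012 for that group.

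**The concern.** On the TVP-1012 clock, the day of an extension visit in P->1 mg depends on two visit dates, each free to move 7 days, so a fully compliant visit can be 14 days off nominal. The Week 3/6 and Week 26/29 edges in the laboratory and vital-sign tables lie only 10 days from nominal. Some samples taken on schedule therefore fall outside the window of the visit they belong to.

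The consequence is clearest at the last visit. P->1 mg has no scheduled visit after VISIT 14, so a Week 29 value in that group is an end-of-treatment value under another label. The subject then contributes nothing to the Week 26 row, and a few subjects appear in a row that corresponds to no planned visit. Laboratory values and vital signs are secondary endpoints in a study whose primary objective is long-term safety, so the end-of-treatment values should stay together.

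**Working it through.** **Inputs.** Visit windows: protocol Appendix A. Start of dosing: protocol 8.1.3. Day 1 for P->1 mg: SAP Glossary. Analysis windows: SAP Definition of Visit Window A). Planned enrolment of 182: protocol 13.3.

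**1. Reproduce the SAP edges.** Cutting midway between adjacent scheduled days (7 x week), with an exact midpoint going to the later window, gives:

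- Week 3/6: (21 + 42)/2 = 31.5, so 31/32.
- Week 26/29: (182 + 203)/2 = 192.5, so 192/193.
- MDS-UPDRS Week 26/32: (182 + 224)/2 = 203, so 202/203.

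The same rule reproduces every laboratory and vital-sign boundary. The 10-day edges arise because Weeks 3 and 29 lie three weeks from their neighbours.

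**2. Convert to the TVP-1012 clock.** Day 1 is VISIT 8 + 1, so TVP-1012 day = visit day - (VISIT 8 day + 1) + 1 = visit day - VISIT 8 day.

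| Visit | Nominal | Earliest | Latest | Filed elsewhere |
|---|---|---|---|---|
| VISIT 9 | 21 | 196 - 189 = 7 | 210 - 175 = 35 | Days 32-35, as Week 6 |
| VISIT 10 | 42 | 217 - 189 = 28 | 231 - 175 = 56 | Days 28-31, as Week 3 |
| VISIT 13 | 140 | 315 - 189 = 126 | 329 - 175 = 154 | none |
| VISIT 14 | 182 | 357 - 189 = 168 | 371 - 175 = 196 | Days 193-196, as Week 29 |

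VISIT 12 (Days 84-112) always files as Week 14. For vital signs only, a single extreme day pair spills at VISIT 10 (Day 56) and at VISIT 11 (Day 84). VISIT 13 ends at Day 154 and Week 26 opens at Day 161, so VISIT 13 cannot fill an empty Week 26. In 1 mg->1 mg, every in-window extension visit files correctly.

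**3. Size at VISIT 14.** Displacement needs a net drift of 11 to 14 days. Of 15 x 15 = 225 day pairs, 4 + 3 + 2 + 1 = 10 qualify, so 10/225 = 4.4% if days are uniform and independent. On an even split, 182/2 = 91 and 0.044 x 91 is about 4 subjects. The documents do not give the split by group.

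- Deviations within 6 days: (2 + 1)/(13 x 13) = 3/169 = 1.8%.
- Deviations within 5 days: the largest net drift is 10, so 0%.

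**4. Weeks 3 and 6.** VISITs 9 and 10 are each displaced in 10/225 pairs on the same assumption. Counting VISITs 9, 10 and 14 together, 12.4% of subjects would have at least one displaced value.

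**5. The last-dose condition.** The tables also require fewer than 8 days since the last dose. Dosing on the morning of the visit, as protocol 8.1.3 instructs, meets this. If the last dose were on Day 182, a Day 193 sample would be 11 days after it and would be dropped, not filed as Week 29. Week 26 is empty either way.

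**The case against.** Windowing by actual exposure day is a legitimate choice, and the SAP applies it consistently. A Day 196 sample is 7 days from Week 29 and 14 from Week 26. A Day 35 sample is 7 days from Week 6 and 14 from Week 3. A reader might infer that samples are reported at the wrong exposure time. The documents do not support that: each value sits at the nearer exposure day and is displaced only relative to its scheduled visit.

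A reader might also infer that the windows are narrower than the visit drift. The drift spans 29 days, while the laboratory windows for Weeks 3, 6 and 26 span 31, 38 and 32 days. The tight part is one edge (10 days against 14), and most on-schedule samples file as expected. Vital-sign Weeks 6 and 10 (24 and 28 days) are narrower in width, but Week 26 is not.

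The rate is also likely to be lower than 4.4%. The two visits must drift in opposite directions, and if later visits are booked from earlier ones the offsets move together. The value is displaced, not discarded, and the small count in the Week 29 row would be visible. The Handling Rules for Analysis Data are not among the documents and may already deal with this.

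All of that stands, and for Weeks 3 and 6 it is decisive: the choice there is between exposure day and visit number, with a cost either way. It does not remove the VISIT 14 problem. No later scheduled visit exists in P->1 mg for a Week 29 row to represent, no end-of-administration row recovers the value, and the SAP's own MDS-UPDRS table keeps the same visit in Week 26.

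**Conclusion.** The point holds for VISIT 14 in P->1 mg and is minor. Some in-window end-of-treatment laboratory and vital-sign values leave the Week 26 row: 4.4% of the group, about 4 of 91, with uniform, independent visit days across the full windows, and none if deviations stay within 5 days. Visit-day distributions, independence and the even split are assumptions. Any subjects lost before VISIT 14 would lower the count. Filing as Week 29, rather than exclusion, depends on the last-dose condition.

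The effect is confined to descriptive by-visit summaries and laboratory shift tables. It would be a mistake to read it as a threat to the primary endpoint: the TEAE analyses in SAP 3.1 do not use these windows, and the overall vital-sign MAV counts in SAP Appendix 2 use all evaluable data up to 7 days after the last dose. The Week 3/6 overlap is a matter of convention, not an error.

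**What to change.** In SAP Definition of Visit Window A), add for P->1 mg laboratory tests and vital signs that the Week 26 window runs from Day 161 to at least Day 202, matching the MDS-UPDRS table, or to the end of follow-up. State that no rows after Week 26 are printed for this group. The latest in-window VISIT 14 is Day 196, so either limit captures every on-schedule value. The last-dose condition can stay as it is; values that fail it would still be excluded.

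For Weeks 3 and 6, moving the cut point cannot separate the visits, because VISIT 9 (Days 7-35) and VISIT 10 (Days 28-56) overlap on Days 28 to 35. At most, note this in the SAP or add a sensitivity listing by visit number.

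The cost is one line of SAP text and one programming condition. No new data are needed and 1 mg->1 mg is unchanged. The downside is that a few Week 26 values will lie up to 14 days after nominal.

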## Vital Signs

Visit	Scheduled Study Time	Visit Windows	
		Number of days after administration	Number of days after the end of administration
Baseline (prior to TVP-1012 administration)	Number of days after administration: -1	-22 ~ -1	
Week 3	Number of days after administration: 21	1 ~ 31	< 8
Week 6	Number of days after administration: 42	32 ~ 55	< 8
Week 10	Number of days after administration: 70	56 ~ 83	< 8
Week 14	Number of days after administration: 98	84 ~ 118	< 8
Week 20	Number of days after administration: 140	119 ~ 160	< 8
Week 26	Number of days after administration: 182	161 ~ 192	< 8
Week 29	Number of days after administration: 203	193 ~ 213	< 8
Week 32	Number of days after administration: 224	214 ~ 237	< 8
Week 36	Number of days after administration: 252	238 ~ 265	< 8
Week 40	Number of days after administration: 280	266 ~ 300	< 8
Week 46	Number of days after administration: 322	301 ~ 342	< 8
Week 52	Number of days after administration: 364	343 ~ 385	< 8

## 12-lead ECG, Weight

Visit	Scheduled Study Time	Visit Windows	
		Number of days after administration	Number of days after the end of administration
Baseline (prior to TVP-1012 administration)	Number of days after administration: -1	-22 ~ -1	
Week 14	Number of days after administration: 98	1 ~ 139	< 8
Week 26	Number of days after administration: 182	140 ~ 230	< 8
Week 40	Number of days after administration: 280	231 ~ 321	< 8
Week 52	Number of days after administration: 364	322 ~ 385	< 8

B) For the analyses based on the data after study drug administration for the treatment period in the preceding study

For MDS-UPDRS Part II + Part III total score among each test, observation, and evaluation items, evaluable data will be handled according to the following rules. The number of days after administration and number of days after the end of administration is defined in “For the analyses based on the data after study drug administration for the treatment period in the preceding study” in Glossary.

Among the visits, at visits other than baseline (at end of observation period) and Week 52 of the Treatment Period (LOCF), evaluable data within the visit window will be used. If more than one evaluable data lies within the same visit window, the examinations, observation, and assessments with the Study Time closest to the scheduled Study Time will be used. If there are two observations equidistant to the scheduled Study Time, the later observation will be used. The size of difference from the Study Time will be determined based on the number of days after administration.

Among the visits, at baseline (at end of observation period) and Week 52 of Treatment Period (LOCF), the data with the largest number of days after administration will be used among the evaluable data within the visit window.

MDS-UPDRS Part II + Part III total score

Visit	Scheduled Study Time	Visit Windows	
		Number of days after administration	Number of days after the end of administration
Baseline (end of observation period)	Number of days after administration: -1	-22 ~ -1	
Week 6 (Treatment Period)	Number of days after administration: 42	1 ~ 55	< 8
Week 10 (Treatment Period)	Number of days after administration: 70	56 ~ 83	< 8
Week 14 (Treatment Period)	Number of days after administration: 98	84 ~ 118	< 8
Week 20 (Treatment Period)	Number of days after administration: 140	119 ~ 160	< 8
Week 26 (Treatment Period)	Number of days after administration: 182	161 ~ 202	< 8
Week 32 (Treatment Period)	Number of days after administration: 224	203 ~ 237	< 8
Week 36 (Treatment Period)	Number of days after administration: 252	238 ~ 265	< 8
Week 40 (Treatment Period)	Number of days after administration: 280	266 ~ 300	< 8
Week 46 (Treatment Period)	Number of days after administration: 322	301 ~ 342	< 8
Week 52 (Treatment Period)	Number of days after administration: 364	343 ~ 385	< 8
Week 52 (Treatment Period) (LOCF)		1 ~ 385	< 8

## Others

- Causality of AEs with study drug:

Cases where the causality with the study drug cannot be ruled out, that is, “Unlikely,” “Possibly,” or “Probably” are handled as “Related,” and cases where the causality with the study drug are “Unrelated” are handled as “Not related.”

- Smoking history:

When the smoking history is “Current smoker,” it is handled as “Yes.” When the smoking history is “Never smoked” or “Ex-smoker,” it is handled as “No.”

\* If the category is set as [Yes or No], it is handled with the aforementioned contents.

- Entry to this study:

If the subject is considered eligible to enter to this study, it is handled as “Yes” and other cases are handled as “No.”

- Duration of study drug administration in this study (days):

Day of last study drug administration in this study - Day of first study drug administration in this study +1

- Duration of study drug administration for the treatment period in both studies (days):

“Day of last study drug administration for the treatment period in the preceding study” or “Day of last study drug administration in this study,” whichever the latest - Day of first study drug administration for the treatment period in the preceding study +1

- Duration of Exposure to TVP-1012 (days):

Day of last TVP-1012 administration - Day of first TVP-1012 administration +1

- Compliance of TVP-1012 (%):

(Prescribed quantity of TVP-1012 - Retrieved quantity of TVP-1012) / Duration of TVP-1012 administration × 100 (rounded to the first decimal place)

- Duration of Parkinson’s disease (years):

([Year when the consent was obtained × 12 + Month when the consent was obtained] – [Onset year of Parkinson’s disease × 12 + Onset month of Parkinson’s disease]) / 12 (rounded to the first decimal place)

\* If the onset month of Parkinson’s disease is missing, the onset month will be imputed as January.

- MDS-UPDRS score:

See Appendix 3 of this Statistical Analysis Plan

- Modified Hoehn and Yahr Scale:

See Appendix 4 of this Statistical Analysis Plan

- PDQ-39 score:

See Appendix 5 of this Statistical Analysis Plan

- QTcF interval (msec):

QT interval (msec) / ( $[RR \text{ interval (msec)} / 1000]^{0.33}$  (rounded to the nearest integer)

